## 11.6. Management of Clinical and Laboratory Adverse Events

If the adverse event is considered related to nivolumab, the investigator must follow the toxicity management guidance outlined in the local label for nivolumab.

## 11.7. Amendment History

A high-level summary of this amendment is provided in tabular form in the subsection below, with changes listed in order of importance. Minor changes such as the correction of typographic errors, grammar, or formatting are not detailed.

Separate summary of change documents for earlier amendments are available upon request.

A separate tracked change (red-lined) document comparing the Protocol Amendment 1 to this amendment will be made available upon the publication of this protocol.

## 11.7.1. Amendment 2 (12 April 2023)

Rationale for Key Changes Included in Amendment 2	Affected Sections	
References to nivolumab were modified throughout the protocol due to Gilead's decision to discontinue nivolumab dosing across study cohorts.	Throughout the protocol, as required	
An ongoing study (GS-US-389-5458) assessing the safety, tolerability and efficacy of once-weekly administration of SLGN 3 mg in special populations with chronic hepatitis B virus (CHB) was added.	Section 1.2.1.1	

Rationale for Key Changes Included in Amendment 2	Affected Sections	
Figure 1 was updated in order to reflect the current changes to study design.	Section 3.2	
A new section to describe the rationale for modifications to the study design was added following the decision to discontinue nivolumab dosing.	Sections 1.3.1	
Benefit/Risk Assessment for nivolumab and Overall Benefit/Risk was updated following discontinuation of nivolumab in this study.	Section 1.5	
Number of viremic chronic hepatitis B (CHB)-infected participants was reduced from 80 to 60 participants to reflect a prior sponsor decision that cohort 3 would not be enrolled.	Synopsis, Section 3.2, and throughout the protocol, as required	
A new subsection for changes to the study design was added.	Section 3.2.1	
All incidences of 'Participants who remain on nucleos(t)ide (NUC) treatment into follow-up (FU) period are not required to attend FU Weeks 2 and 8 visits' have been removed as all participants in Cohort 1 will remain on NUCs throughout the FU period.	Synopsis and Section 6.7	
FU period was updated to outline the procedures following the change to study design.	Synopsis and Section 3.5	
An individual treatment modification criterion ( Any on treatment uveitis, confirmed by ophthalmologic evaluation ) was moved to individual treatment discontinuation criteria after confirmation that no rechallenge is required following the resolution of the AE.	Synopsis and Section 6.9.1	
A new section for toxicity management of irAEs observed with nivolumab was added.	Section 11.5	
AE of special interest (eg, uveitis) was added to the safety analysis.	Section 8.6.2	
FU Week 8 virtual/telephonic visit pregnancy test was changed across all cohorts.	Section 11.3 and throughout the protocol, as required.	
The visit windows for FU Weeks 24 through FU Week 48 (for Cohorts 1 and 2) were extended to $\pm$ 14 days.	Sections 11.3 and 6.7	
FU Week 2 was removed in order to simplify the FU period for participants.	Section 11.3 and throughout the protocol, as required	
References to Cohort 3 were removed throughout the protocol due to the decision to discontinue this cohort.	Throughout the protocol, as required	
Incidences of Global Patient Safety have been changed to Patient Safety (PS).	Section 7 and throughout the protocol, as required	
Minor changes included to correct typographical errors.	Throughout the protocol, as required	

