## Selgantolimod

Selgantolimod treatment alone have been evaluated in multiple Phase 1 and Phase 2 studies in both healthy volunteers and participants with CHB. The longest durations of treatment were evaluated in 2 Phase 2 studies, GS-US-389-2024 (NUC-suppressed participants with CHB) and GS-US-389-2025 (treatment-naive participants with CHB), that administered placebo, SLGN 1.5 mg, or 3 mg once weekly with a NUC for 24 weeks to 93 participants with CHB. Selgantolimod up to 3 mg once weekly was safe and well tolerated in 102 participants with CHB (48 participants in Study GS-US-389-2024 and 54 participants in Study GS-US-389-2025). Based on pooled safety review of the SLGN studies, 3 potential ADRs related to SLGN of nausea, vomiting, and iridocyclitis were identified. Majority of these ADRs reported have been mild or moderate in severity. To mitigate the impact of ADR of nausea and vomiting for SLGN, the use of antiemetic (eg., ondansetron) is allowed in the study. A Grade 2 iridocyclitis (in the SLGN 1.5-mg dose group) was the only SAE reported that was considered related to SLGN by the investigator and led to early study drug discontinuation. This occurred in a participant who tested positive for the human leukocyte antigen (HLA)-B27 haplotype, a genetic risk factor associated with various immune disorders including anterior uveitis. No Grade 3 or 4 AEs considered related to SLGN treatment have been reported in the studies, except for 1 Grade 3 AE of rhinorrhea considered possibly related by the investigator that was reported in Study GS-US-389-2025. Additional safety results can be found in the IB for SLGN.

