## 6.9. Assessments for Early Discontinuation of Study Treatment

## 6.9.1. Criteria for Discontinuation of Study Treatment

Study treatment(s) that are considered related by the investigator to any of the below event(s) will be held in a participant until resolution of the event:

- Any study drug-related AE  $\geq$  Grade 3
- A confirmed, clinically significant laboratory test abnormality (other than ALT) ≥ Grade 3 considered study drug(s) related by the investigator

Study treatment(s) may be reinitiated following resolution of the above event(s) after discussion with the medical monitor. Study treatment(s) should be restarted in line with their preassigned schedules.

Study treatment(s) that are considered related by the investigator to any of the below events will be permanently discontinued:

- Any on-treatment uveitis, confirmed by ophthalmologic evaluation
- Any confirmed recurrence of study drug—related Grade 3 or 4 (excluding laboratory abnormalities) AE following dose interruption mandates permanent discontinuation of study drug(s)
- Unacceptable toxicity or toxicity that, in the judgment of the investigator, compromises the ability to continue study-specific procedures or is considered not to be in the participant's best interest
- Any study drug-related Grade 4 AE (excluding laboratory abnormalities)
- Any study drug—related ≥ Grade 3 AE not able to be medically managed (eg, nausea with antiemetics)
- Any confirmed study drug-related laboratory abnormality  $\geq$  Grade 3 following rechallenge
- A clinically significant Grade 4 laboratory abnormality
- Virological breakthrough: as defined in Section 2

Additional criteria for permanent discontinuation of study treatment(s):

- Intercurrent illness that would, in the judgment of the investigator, affect assessments of clinical status to a significant degree
- Hepatic disease progression or lack of efficacy defined as participants in Cohorts 1 and 2 (Group A) who do not achieve HBsAg decline ≥ 0.2 log10 IU/mL at Week 12
- Participant requests to discontinue for any reason
- Participant noncompliance
- Pregnancy during the study
- At the discretion of the investigator, Gilead, a regulatory agency or an institutional review board (IRB), or independent ethics committee (IEC).

If a participant discontinues study dosing (eg, as a result of an AE), every attempt should be made to keep the participant in the study and continue to perform the required study-related FU and procedures.

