## 7.7.1. Grades 1 and 2 Laboratory Abnormality or Clinical Event

Continue study drug at the discretion of the investigator.

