## 7.7.2. Grade 3 Laboratory Abnormality or Clinical Event

- For Grade 3 laboratory abnormality or clinical event, study drug may be continued if the event is considered to be unrelated to study drug
- For any study drug-related, Grade 3 AE, study drug should be held
- For any study drug—related ≥ Grade 3 AE not able to be medically managed (eg, nausea with antiemetics), study drug should be permanently discontinued
- For a confirmed laboratory abnormality, study drug—related Grade 3, study drug would be held until toxicity returns to ≤ Grade 2. If a laboratory abnormality recurs to ≥ Grade 3 following rechallenge, study drug should be permanently discontinued, and the participant managed according to local practice. Recurrence of laboratory abnormalities considered unrelated to study drug may not require permanent discontinuation.

• For a Grade 3 clinical event, or clinically significant laboratory abnormality confirmed by repeat testing within 3 calendar days that is considered to be related to study drug, study drug should be withheld until the toxicity returns to ≤ Grade 2

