Pediatric < 14 Years	Wheezing OR minimal increase in respiratory rate for age	Nasal flaring OR Intercostal retractions OR Pulse oximetry 90% to 95%	Dyspnea at rest causing inability to perform usual social & functional activities OR Pulse oximetry < 90%	Respiratory failure with ventilatory support indicated	

OCULAR/VISUAL					
	Grade 1	Grade 2	Grade 3	Grade 4	
Uveitis	Asymptomatic but detectable on exam	Symptomatic anterior uveitis OR Medical intervention indicated	Posterior or pan-uveitis OR Operative intervention indicated	Disabling visual loss in affected eye(s)	
Visual Changes (from baseline)	Visual changes causing no or minimal interference with usual social & functional activities	Visual changes causing greater than minimal interference with usual social & functional activities	Visual changes causing inability to perform usual social & functional activities	Disabling visual loss in affected eye(s)	

SKIN				
	Grade 1	Grade 2	Grade 3	Grade 4
Alopecia	Thinning detectable by study participant or caregiver (for disabled adults)	Thinning or patchy hair loss detectable by health care provider	Complete hair loss	NA
Cutaneous Reaction – Rash	Localized macular rash	Diffuse macular, maculopapular, or morbilliform rash OR Target lesions	Diffuse macular, maculopapular, or morbilliform rash with vesicles or limited number of bullae OR Superficial ulcerations of mucous membrane limited to one site	Extensive or generalized bullous lesions OR Stevens-Johnson syndrome OR Ulceration of mucous membrane involving two or more distinct mucosal sites OR Toxic epidermal necrolysis (TEN)
Hyperpigmentation	Slight or localized	Marked or generalized	NA	NA
Hypopigmentation	Slight or localized	Marked or generalized	NA	NA
Pruritis (itching – no skin lesions) (See also Injection Site Reactions: Pruritis associated with injection)	Itching causing no or minimal interference with usual social & functional activities	Itching causing greater than minimal interference with usual social & functional activities	Itching causing inability to perform usual social & functional activities	NA

GASTROINTESTINAL				
	Grade 1	Grade 2	Grade 3	Grade 4
Anorexia	Loss of appetite without decreased oral intake	Loss of appetite associated with decreased oral intake without significant weight loss	Loss of appetite associated with significant weight loss	Life-threatening consequences OR Aggressive intervention indicated (eg, tube feeding or total parenteral nutrition)

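### Confirmed on-treatment uveitis is a permanent stop at any grade in the Synopsis and Section 6.9.1, but the general toxicity rules in Section 7.7 still allow continuing at Grades 1 and 2 and prescribe a hold at Grade 3

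*Supplement*

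**What the plan says.** Section 6.9.1 introduces its second list with "Study treatment(s) that are considered related by the investigator to any of the below events will be permanently discontinued", and that list includes "Any on-treatment uveitis, confirmed by ophthalmologic evaluation". The Synopsis carries the same criterion under its individual treatment discontinuation criteria. Neither place sets a grade.

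The first list in Section 6.9.1, repeated in the Synopsis, covers events for which treatment is only held. It includes any drug-related adverse event of Grade 3 or higher. Treatment may be started again once the event has resolved, after discussion with the medical monitor.

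Section 7.7 applies to all clinical toxicities and works by grade. For Grades 1 and 2 the whole of Section 7.7.1 reads "Continue study drug at the discretion of the investigator". For a related Grade 3 clinical event Section 7.7.2 says "study drug should be withheld until the toxicity returns to ≤ Grade 2". Section 7.7.3 ends in permanent discontinuation for a Grade 4 clinical event. A bullet in Section 7.7 covers the dose to use when restarting after an event resolves.

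Appendix 11.5 has its own row for uveitis. Grade 1 is "Asymptomatic but detectable on exam". Grade 2 is symptomatic anterior disease or a need for medical treatment, Grade 3 is posterior or pan-uveitis or a need for surgery, and Grade 4 is disabling loss of vision.

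The Amendment 2 table in Section 11.7.1 records that the uveitis criterion "was moved to individual treatment discontinuation criteria after confirmation that no rechallenge is required following the resolution of the AE" and gives the affected sections as "Synopsis and Section 6.9.1".

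**The concern.** A confirmed, related uveitis falls under two sets of instructions. One turns on the diagnosis and ends in a permanent stop. The other turns on the grade and, below Grade 4, allows treatment to go on or be resumed. Section 7.7 does not mention uveitis as an exception, although it repeats other permanent-stop triggers from Section 6.9.1: Grade 4 events, Grade 3 events that cannot be medically managed, and recurrence after interruption. A site working from Section 7.7 could reasonably take its list of stops as complete.

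The event is not a remote one for this drug. Sections 1.2.1 and 1.5 name iridocyclitis among the adverse reactions to selgantolimod, and Section 1.5 reports that "A Grade 2 iridocyclitis (in the SLGN 1.5-mg dose group) was the only SAE reported that was considered related to SLGN". Uveitis is the only adverse event of special interest that Section 8.6.2 gives by name. The scheduled ophthalmologic examinations in Section 6.6 can also find disease without symptoms, which is Grade 1.

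At stake are consistent handling of a safety event, exposure to selgantolimod after it, and the Section 8.6.2 summaries of treatment-emergent events leading to discontinuation or to temporary interruption. The same event could be counted in one summary, the other, or neither, depending on which section the site followed.

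**Working it through.** No arithmetic applies. The check sets the current passages side by side for one case: uveitis on treatment, confirmed on eye examination, and judged related by the investigator.

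| Grade (Appendix 11.5) | Synopsis and Section 6.9.1, uveitis criterion | Section 7.7 | Result |
|---|---|---|---|
| 1 | Permanent stop | 7.7.1: continuing is left to the investigator | 7.7.1 allows what 6.9.1 rules out |
| 2 | Permanent stop | 7.7.1: same | Same |
| 3 | Permanent stop | 7.7.2: hold until Grade 2 or lower; permanent stop if the event cannot be medically managed; 7.7 adds recurrence after interruption | Different instruction unless one of those exceptions applies |
| 4 | Permanent stop | 7.7.3: permanent stop for a Grade 4 clinical event | Agree |

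Three further steps follow.

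1. **Section 6.9.1 overlaps with itself at Grade 3.** A related Grade 3 uveitis meets the hold list (related event of Grade 3 or higher) and the permanent-stop list (confirmed uveitis). The two holds also end at different points: resolution in Section 6.9.1, Grade 2 or lower in Section 7.7.2. On the Appendix 11.5 scale, Grade 2 can still be symptomatic anterior uveitis.
2. **Is an order of precedence stated?** Section 3.6 refers the reader to Section 6.9 for discontinuation criteria. The overall benefit/risk text in Section 1.5 says that the parameters for modification, interruption or discontinuation are in Section 6.9.1. Both say where the criteria stand; neither says that they override Section 7.7. Section 7.7 does not refer back to Section 6.9.1.
3. **Does another passage settle it?** Section 7.7 sends the reader to Appendix 11.6 for uniform guidelines, but that appendix only directs events related to nivolumab to the local label. Sections 7.7.1 to 7.7.3 are therefore the working rules for the other study drugs.

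The amendment table is not the fault. It matches the current Synopsis and Section 6.9.1. It only suggests how the mismatch arose, since Section 7.7 is not among the sections it lists for this change.

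**The case against.** The best reply is that the specific rule governs the general one. Sections 1.5 and 3.6 make Section 6.9 the home of the stopping criteria, and Section 6.9.1 already sets specific permanent stops beside a general hold. Section 7.7.1 is permissive, so a site that stops treatment at Grade 1 or 2 breaches nothing in it. At Grade 3, Section 7.7.2 prescribes a hold but does not order a restart; the restart wording in Section 7.7 and Section 6.9.1 is conditional. A site that follows the uveitis criterion can thus satisfy every section. The one related serious case described in Section 1.5 did lead to early discontinuation of study drug.

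Much of this stands, and it limits the point. The documents do not support a claim of opposite orders at three grades, which a reader might infer: the difference is between a required stop and a permitted continuation (Grades 1 and 2) or a hold with possible restart (Grade 3). Nor do they support reading the amendment as having changed Section 6.9.1 alone, because the Synopsis was changed too. Section 6.9.2 does not send uveitis to Section 7.7; its pointer concerns ALT elevation or flare.

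What the reply does not remove is that compliance runs one way only. A site that relies on Section 7.7 may continue, or hold and restart, in keeping with that section and yet depart from Section 6.9.1. The specific-over-general reading is sensible, but the protocol leaves the reader to supply it.

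**Conclusion.** The point holds as an unreconciled safety instruction. For confirmed, related, on-treatment uveitis, the Synopsis and Section 6.9.1 differ from Sections 7.7.1 and 7.7.2 at Grades 1, 2 and 3 and agree at Grade 4. The clearest tension is at Grade 3, where the hold list in Section 6.9.1 also applies. This rests on reading the general rules in Section 7.7 as covering uveitis, which their scope and the Appendix 11.5 grades support, and on the absence of a stated exception or precedence.

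It should be mended, but its statistical reach is small: the Section 8.6.2 summaries it touches are descriptive counts.

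A reader might want to put a probability on such an event from the single serious case in Section 1.5. The documents do not support a useful figure. The case arose at 1.5 mg in an HLA-B27-positive participant, whereas this trial uses 3 mg. Section 1.5 gives both 93 and 102 participants for the two studies concerned. By Amendment 2, enrollment was complete and Group B treatment was being stopped, so the planned 100 is not the number still at risk under the current text. The finding does not depend on such a figure.

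**What to change.** Reconcile the Synopsis, Section 6.9.1 (including the hold list for related events of Grade 3 or higher, which the Synopsis repeats), Section 7.7 with its restart bullet, and Sections 7.7.1 and 7.7.2, so that confirmed on-treatment uveitis has one instruction at each grade. A cross-reference in Section 7.7 naming the section that governs uveitis would do, or a sentence stating the order of precedence between Sections 6.9.1 and 7.7. Which rule stands is for the sponsor to decide.

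The cost is a few sentences of text and a notice to sites. Sample size, visit schedule and data collection are unaffected. If any uveitis was handled before the notice, the study report should say which section the site followed, so that the discontinuation and interruption counts can be read correctly.
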